#### 4.5.3. Medical history

The medical history conditions will be summarized by treatment group for the Safety Analysis Set as frequencies and percentages according to the System Organ Class (SOC) and Preferred Term (PT) levels.

Medical history will be sorted by decreasing order of frequency by SOC and PT of the Total group. The listing will display the SOC, PT, and the verbatim text from the study Investigators.

## 4.6. Efficacy Evaluation

Efficacy analyses will be conducted using the FAS population. The co-primary efficacy endpoints will, additionally, be analysed on the PP analysis set and on the mFAS analysis set (if at least 20% of subjects from the FAS used relevant treatments within the 28 days before screening). The statistical methods will focus on summarizing the data collected by visit using appropriate tabular and graphical presentations. Diary data, individual items and scores for questionnaires will be displayed in listings. Plots will be produced for some endpoints, as detailed in the following sections.

#### 4.6.1. Co-primary analysis

The co-primary endpoints are the change from baseline in the mean daily frequency and mean weekly severity of moderate and severe hot flushes at Weeks 4 and 12.

For each timepoint (Baseline, Week 1, Week 2, Week 4, Week 8, Week 12) summaries will be produced which use data from the 7 days with at least one available eDiary data entry in the evening and/or the morning before the Visit date:

- These 7 days do not need to be consecutive.
- As the data entered in the morning diary is assigned to the previous calendar day (a diary day comprises an evening and a morning entry, in that order) the morning diary with the same calendar date as the Visit day may be included in the calculation.
- For Week 1, the first 7 post-baseline days with at least one available data in the evening and/or the morning will be used.

The methods for calculating the endpoint are the same as described in section 4.2.11.

Absolute and changes from baseline in the mean daily frequencies and mean weekly severity of moderate and severe hot flushes will be summarised by treatment group. Percent changes from baseline in the mean daily frequencies will be also summarised.

The change from baseline will be calculated as follow:

Mean daily frequency (or mean severity) at week 4 (or Week 12) – Mean daily frequency (or mean severity) at baseline.

The percent change from baseline will be calculated as follow:

(Change from baseline / Mean daily frequency at baseline) \* 100.

The mean change from baseline and the corresponding 95% confidence interval (CI) will be displayed graphically by visit on the observed values and by treatment groups.

Bar graphs of the change from baseline at Week 4 and Week 12 will be produced for each treatment group.

The change from baseline endpoint will be analysed using a Mixed-Effect Model Repeated Measures (MMRM) incorporating post-randomization data collected up to treatment discontinuation at weeks 12 (Week 1, 2, 4, 8 and 12 will be included; Week 16 visit data will not be included in the model) and with consideration of the variance-covariance matrix of the repeated measures.

This method allows for a general unstructured variance-covariance matrix and will include data from subjects with incomplete data from some scheduled time points. The model will be implemented in SAS using the MIXED procedure and will include the change from baseline as the dependent variable. The fixed effects in the model will include independent variables of randomized treatment, visit (nominal post-baseline visits as per the schedule of assessments) and treatment-by-visit interaction, along with the following baseline covariates: Baseline frequency or severity, Region (section 4.2.3). Visits will be treated as a repeated variable within a patient. Patient, treatment and visit will be treated as factor variables. An unstructured variance-covariance structure will be applied to model the within-patient errors. The model will be fitted using the Restricted Maximum Likelihood (REML) method. Denominator degrees of

freedom will be estimated using Kenward-Roger's approximation.

Pairwise statistical comparisons are planned for each NT-814 dose group (40 mg, 80 mg, 120 mg and 160 mg) versus placebo. To estimate the difference between the treatment groups in mean change from baseline to Week 4 and Week 12, a treatment-by-visit interaction contrast will be constructed (i.e., the treatment group contrast at Week 4 and 12). On the basis on this analysis, least square means, standard errors, and the 95% confidence interval for the treatment difference (at Week 4 / 12, primary endpoint timepoints) will be reported.

SAS code:

```
PROC MIXED DATA= dataset;  
CLASS region avisitn treat subjid;  
MODEL chg=base treat region avisitn treat*avisitn / ddfm=KENWARDROGER;  
REPEATED avisitn / subject=subjid type=un;  
LSMEANS treat*avisitn / cl pdiff;  
ODS OUTPUT lsmeans=lsmeans_ tests3 = tests3_ diffs = diffs_  
convergenceStatus=convergenceStatus_  
WHERE avisitn > xx;  
RUN;  
* chg represents the mean change from baseline variable;  
* base represents the mean daily frequency (or severity) at baseline;  
* treat represents the treatment group;  
* avisitn represents the analysis visits as defined in section 4.2.12. Only the  
post-baseline visits must be included  
* region represents the categorical covariate related to stratification factors;  
Further options to control the output may be added.  
From ODS OUTPUT, using the correct visit/treatment selection, the outputs will  
allow getting the following:  
- lsmeans_: LSM, SE and 95% CI for each treatment at each visit  
- diffs_: Difference in LSM, 95% CI and p value  
- tests3_: overall p values for the fixed effects.
```

The assumption of normality (to ensure that the parametric models are appropriate) will be explored via the visual checks that are based on a normal probability plot of the residuals against their values expected on the normal distribution. If the data are normally distributed then the residuals will roughly form a straight line on the normal plot. If the plotted data deviates markedly from a straight line then it is likely that the data are not normally distributed. In that case, a non-parametric analysis will be used as a sensitivity analysis to complement the parametric MMRM results. A Wilcoxon rank-sum test will be performed at each timepoint (Week 4 and 12) and for each pairwise treatment comparison.

SAS code:

```
PROC NPARIWAY DATA= dataset WILCOXON;  
CLASS treat;  
VAR chg;  
EXACT Wilcoxon;  
WHERE avisit = "Week 4" and treat in ("Placebo","NT-814 40mg");  
RUN;  
* chg represents the mean change from baseline variable;  
* treat represents the treatment group;  
* avisit represents the analysis visits as defined in section 4.2.12.
```

In addition, as a sensitivity analysis, an analysis of covariance (ANCOVA) including terms for treatment group, along with the following baseline covariates: Baseline frequency or severity, Region (section 4.2.3). This analysis will be performed at each timepoint (Week 4 and Week 12).

SAS code:

```
PROC MIXED DATA=dataset;
CLASS treat region;
MODEL chg = treat base region;
LSMEANS treat / pdiff (ref='Placebo') cl;
ODS OUTPUT lsmeans=lsmeans_ tests3 = tests3_ diffs = diffs_
convergenceStatus=convergenceStatus_;
WHERE avisit = "Week 4";
RUN;
* base represents the baseline value of the endpoint;
* chg represents the change from baseline variable;
* treat represents the treatment group;
* region represents the categorical covariate related to stratification factors.
Further options to control the output may be added. See MMRM notes for ODS
OUTPUT.
```

As an ad-hoc analysis, treatment mean comparisons to placebo may be made via estimated means from a 4-parameter Emax model fit and trend test for increasing response with increasing dose based on isotonic regression modelling at Week 4 and Week 12 using the same methodology as described in section 4.3.2.

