### 3. SUBJECT POPULATIONS

#### 3.1. Population Definitions

The following subject populations will be evaluated and used for presentation and analysis of the data:

**Screen Analysis Set:** the screened population will include all subjects with informed consent.

**Randomized Analysis Set:** the randomized population will include all subjects with a randomization date and number.

**Safety Analysis Set:** All subjects who receive at least one dose of double-blind study drug irrespective of treatment received. Subjects will be analysed according to treatment received.

**Full Analysis Set (FAS):** All randomised subjects who received at least one dose of double-blind study drug, irrespective of treatment received, and have hot flush data for at least 7 days' worth of post-treatment assessments (i.e. requirement for the primary efficacy endpoint). Subjects will be analysed according to randomised treatment. This is the primary efficacy analysis set for the study.

**Modified Full Analysis Set (mFAS):** All subjects in the FAS excluding those who took non-hormonal treatments (anti-depressants, alpha-2 agonists, gabapentinoids and cannabis) or over the counter herbal treatments (intended to treat menopausal symptoms) that may have had a confounding effect on hot flash frequency and/or severity at any time during the study (defined as within 28 days before the start of Screening Visit 2 through to the Week 12 visit, inclusive). The medications entered in EDC have been reviewed by Sponsor's blinded Medical Expert, and the following final list of PREFERRED NAME was confirmed:

CLONIDINE  
CLONIDINE HYDROCHLORIDE  
CIMICIFUGA RACEMOSA  
TRIFOLIUM PRATENSE  
CIMICIFUGA RACEMOSA;HYPERICUM PERFORATUM  
CANNABIS SATIVA  
GABAPENTIN  
PREGABALIN  
AMITRIPTYLINE  
NORTRIPTYLINE  
CITALOPRAM  
CITALOPRAM HYDROBROMIDE  
ESCITALOPRAM  
ESCITALOPRAM OXALATE  
FLUOXETINE  
FLUOXETINE HYDROCHLORIDE  
PAROXETINE  
PAROXETINE HYDROCHLORIDE  
SERTRALINE  
SERTRALINE HYDROCHLORIDE  
BUPROPION  
BUPROPION HYDROCHLORIDE  
DESVENLAFAXINE  
DESVENLAFAXINE SUCCINATE

DULOXETINE  
DULOXETINE HYDROCHLORIDE  
VENLAXAFINE  
VENLAFAXINE HYDROCHLORIDE  
MIRTAZAPINE  
TRAZODONE  
TRAZODONE HYDROCHLORIDE  
VORTIOXETINE HYDROBROMIDE  
CALCIUM;CIMICIFUGA RACEMOSA EXTRACT;GENISTEIN;HERBAL EXTRACT  
NOS;MAGNESIUM;PIPER METHYSTICUM RHIZOME

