### 3.2. Protocol Deviations

Protocol deviations are defined as a deviation from the approved protocol.

Prior to database lock, NeRRe will be responsible for producing the final protocol violation file (formatted as a Microsoft Excel file), in collaboration with the data monitoring group; this file will include a description of the protocol violation and the categorization as minor/major, relevant / not relevant. Deviations classified as relevant will result in exclusion of the subject from the Per Protocol Population. This file will be finalized and signed prior to hard database lock, after the blinded data review meeting (BDRM).

In addition, the following protocol deviations will be programmatically derived by Cytel:

- 1) Category = Non-compliance with diary completion
  - PD Reference 3.9: Less than 70% compliance with hot flush diary completion at Baseline (Visit 3).
  - PD Reference 3.10: Less than 70% compliance with hot flush diary completion at Week 4 (Visit 5).
  - PD Reference 3.11: Less than 70% compliance with hot flush diary completion at Week 12 (Visit 7).
  - PD Reference 3.12: Less than 70% compliance with hot flush diary completion at Week 2 (Visit 4), Week 8 (Visit 6) or Week 16 (Visit 8).

Compliance will be calculated for Baseline, Week 2, Week 4, Week 8, Week 12 and Week 16, using the same 7 days (or less than 7 days if this is the case per the rules defined in section 4.3.2) used in the analysis of HF frequency & severity.

The 70% cut-off essentially means that at least 10 of the 14 possible diary entries will need to have been completed for the subject to be in the PP population.

2) Category = Non-compliance with study medication

PD Reference 4.2: Subject <80% compliant with once-daily dosing of IMP.

IMP compliance will be based on the number of capsules taken (section 4.8.1). The compliance calculation should be across the whole 12-week double-blind treatment period (not visit specific). IMP should not be missing.

Relevant protocol deviations will be summarised by treatment group for the Randomised Analysis Set. All protocol violations will be presented in the data listings.

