#### 4.2.12. Visit Windows

Visit windows are defined in Table 2, and are applicable for efficacy (except diary data) and safety.

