#### 4.3.2. Efficacy analysis

At each interim review, summaries by dose group will be provided on the FAS for each of the following:

- Mean daily frequency of moderate and severe HF at baseline, mean daily frequency of moderate and severe HF at each study week, including Week 4 and mean change and percent change from baseline in the mean daily frequency of moderate and severe HF at each study week.
- Mean severity of moderate and severe HF at baseline, mean severity of moderate and severe HF at each study week, including Week 4, and mean change from baseline in the severity of moderate and severe HF at each study week.

If available, summaries of the same data at later time-points (Week 8 and Week 12) will also be reviewed.

Mean daily frequency at each study visit will be calculated using the same method as the one described in section 4.2.11 based on the last 7 days with at least one available data in the evening and/or morning before the corresponding visit.

Mean weekly severity at each study visit will be calculated using the following:

$$\frac{[(\text{number of mild hot flushes for 7 days}) \times 1 + (\text{number of moderate hot flushes for 7 days}) \times 2 + (\text{number of severe hot flushes for 7 days}) \times 3]}{\text{total number of mild, moderate and severe hot flushes over 7 days}}$$

If the number of hot flushes is equal to 0, then the mean severity will be set to 0.

These 7 last days with available data should be within the 14 days prior to the CRF study visit, so in the following window: [CRF Visit date – 14; CRF Visit date], with at least one day within

the last 7 days prior to the study visit. In case of withdrawal, the day this ET visit happened will be checked to see in which windows it is and then to assign the corresponding timepoint. If a CRF visit has already been done at that timepoint, then the CRF visit date will be used. If less than 7 days fulfil these rules, only the correct data will be used in the derivation, and formula will be adjusted using the right number of days as denominator. Morning diary data on the day of a Visit will be included in the derivation as the morning diary is actually associated with the previous calendar day (a complete day is an evening then a morning diary).

In addition, emerging data will be evaluated via the two adaptive following algorithms to evaluate the emerging data at Week 4:

- (i) a Bayesian adaptive Emax (S-shaped) dose-response model fit, and

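### The SAP's Week 1 diary value has no last day, so for women with wholly blank diary days it runs past Day 7 and can overstate early improvement by an unknown, probably small amount

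*SAP*

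**What the plan says.** SAP 4.6.1 (Co-primary analysis) sets the Week 1 rule: "For Week 1, the first 7 post-baseline days with at least one available data in the evening and/or the morning will be used". It adds of the seven days in general: "These 7 days do not need to be consecutive". SAP 4.6.2.1 repeats the Week 1 rule for the secondary frequency, severity and score endpoints. A diary day is an evening entry plus the next morning's entry, and either one is enough for the day to count.

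The limits that exist elsewhere do not reach Week 1:

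- **Look-back limit (SAP 4.3.2):** "These 7 last days with available data should be within the 14 days prior to the CRF study visit". It hangs on a CRF visit date, and the schedule of assessments (SAP 2.4, Table 1) goes from Baseline straight to Week 2.
- **Reduced divisor (SAP 4.3.2):** "If less than 7 days fulfil these rules, only the correct data will be used in the derivation". This belongs to the same visit-anchored rule.
- **Analysis windows (SAP 4.2.12):** "Visit windows are defined in Table 2, and are applicable for efficacy (except diary data) and safety". Table 2 also has no Week 1 row.
- **Diary compliance (SAP 3.2):** "Compliance will be calculated for Baseline, Week 2, Week 4, Week 8, Week 12 and Week 16". Week 1 is not in the list.
- **Full Analysis Set (SAP 3.1):** subjects must "have hot flush data for at least 7 days' worth of post-treatment assessments", so the quota of seven days is eventually filled for everyone analysed, however late.

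Week 1 is a secondary time point (SAP 2.5.1.2), appears in the plots over time, and is one of the five repeated measures in the co-primary MMRM. The model estimates to be reported are for Weeks 4 and 12 (SAP 4.6.1 and 4.6.2.1).

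**The concern.** At clinic visits the SAP uses whatever days qualify inside a bounded window and shrinks the divisor. At Week 1 it reaches forward until it has seven days. Every wholly blank day in the first week is replaced by a later one, so the label no longer describes the days used. Protocol 8.2 defines the endpoint as change to Week 1.

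The direction matters because Week 1 is the earliest efficacy time point and would carry any statement about speed of onset. Protocol 5.2 reports that another NK3 antagonist reached its maximum improvement within two weeks. If NT-814 behaves similarly, days after Day 7 may sit higher on the onset curve than the days they replace.

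**Working it through.** **Related stated figure.** The 70% compliance cut-off is 0.70 × 14 = 9.8, so 10 entries, which agrees with SAP 3.2 ("at least 10 of the 14 possible diary entries will need to have been completed"). Ten entries leave four blank, hence at most two wholly blank days in seven. That would bound the problem, but the check is not made at Week 1.

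**Inputs.** From the documents: the Week 1 rule, and planned reductions of 4 per day on placebo and 8 on the highest dose (SAP 4.1), a difference of 4. Assumed, because neither document gives them: the share *p* of days with at least one entry, independent from day to day, and the shape of onset.

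**How far Week 1 runs.** Counting the first post-baseline diary day as Day 1, the chance of passing Day 7 is 1 − p⁷, and the mean last day is 7/p.

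| p | Chance of passing Day 7 | Mean last day |
|---|---|---|
| 0.99 | 6.8% | 7.1 |
| 0.96 | 24.9% | 7.3 |
| 0.90 | 52.2% | 7.8 |
| 0.80 | 79.0% | 8.8 |

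A day is lost only if both entries are blank. If a share *e* of entries is made and misses are independent, p = 1 − (1 − e)². Then e = 0.90 gives p = 0.99, and e = 0.80 gives p = 0.96. If evening and morning misses always coincide, p = e. So 90% completion of entries means anywhere from about 7% to 52% of women running past Day 7. The excess is usually short: at p = 0.90, 95% of values end by Day 9. Passing Day 14 has probability below 0.1% at p = 0.90 and 0.2% at p = 0.80.

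**Overlap with Week 2.** For a Day 15 visit, diary Days 1 to 14 are available. With *m* of them blank (m up to 7), the first seven and last seven available days share 7 + 7 − (14 − m) = m days. Blanks in Days 1–7 cause overlap through the Week 1 rule. Blanks in Days 8–14 cause it through the Week 2 look-back.

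**Shift in the drug-placebo difference.** The k-th available day falls on average at day k/p, and the mean over k = 1 to 7 is 4/p. If the difference rises linearly to 4 at Day 14, the Week 1 value is (4/14) × (4/p) = 1.143/p, against a true Day 1–7 mean of 1.143. The relative shift is therefore 1/p − 1. The flattening after Day 14 does not change the rounded results at these values of p. The other rows average the assumed curve over the negative binomial distribution of the days used.

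| Assumed difference on day d | True Days 1–7 | p = 0.90 | p = 0.80 |
|---|---|---|---|
| Linear to 4 at Day 14 | 1.14 | 1.27 (+11%) | 1.43 (+25%) |
| Linear to 4 at Day 7 | 2.29 | 2.46 (+7.5%) | 2.63 (+15%) |
| 4(1 − e^(−d/3)) | 2.70 | 2.80 (+4%) | 2.91 (+8%) |
| Linear to 4 at Day 3 | 3.43 | 3.49 (+2%) | 3.54 (+3%) |
| Fast active, slow placebo: 8(1 − e^(−d/1.5)) − 4(1 − e^(−d/14)) | 5.84 | 5.87 (+0.5%) | 5.89 (+0.8%) |

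At p = 0.99 the first row gives +1%. In the last row, at p = 0.50, the shift is −0.05 per day.

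**The case against.** The strongest reply is that the bias rests on two things the documents do not supply. The two-week figure in Protocol 5.2 is an upper bound on time to maximum effect and concerns a different drug, while Protocol 5.1.3 reports that NT-814 reaches steady state within 7 days. Faster onset shrinks the shift, as the table shows, though it does not remove it while early rising days are being replaced by plateau days. The either-entry rule also keeps wholly blank days rare unless women skip whole days. Both points stand, and they are why the size can only be given as a range starting near zero.

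Four stronger readings are tempting and are not supported:

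- **That Week 1 will overstate onset.** Only that it can. A later-rising placebo response can cancel or slightly reverse the shift in the difference.
- **That the co-primary result is biased.** Week 1 enters that model as one repeated measure, and the planned contrasts are at Weeks 4 and 12. Any effect there is indirect, and nothing here quantifies it.
- **That the error favours one arm.** This would need unequal diary completion between arms, for which the documents give no figures.
- **That awakenings share this rule.** Their paragraph in SAP 4.6.2.1 uses the last seven days before the corresponding visit and states no Week 1 rule. That is a separate gap.

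**Conclusion.** The point holds as a defect of definition. Followed exactly, the SAP puts days after Day 7 into Week 1 for any woman with a wholly blank day in that week, and nothing else in either document stops it. If response is still rising, this can overstate Week 1 improvement.

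The size is unknown. Under the assumed curves, the shift in the difference runs from about zero to +11% at 90% completion (+1% on the steepest curve if that 90% refers to entries missed independently), and up to about +25% with 80% of days completed and a linear rise to Day 14. These figures assume days are missed at random and equally in both arms. Because Week 1 is secondary and mainly descriptive, this is a minor correction, worth making before Week 1 is used to describe onset.

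**What to change.** In SAP 4.6.1 and 4.6.2.1:

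- Define Week 1 as the first seven post-baseline calendar diary days only, and say whether the Day 1 evening entry starts the first of them. If it does not, a complete diary already ends on Day 8.
- Divide by the number of those days with data, as SAP 4.3.2 already does for visits.
- Set the value to missing if none, or fewer than a stated minimum, have data.
- State the same Week 1 definition for awakenings.

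With days missed at random, the upward shift becomes zero, since every one of the seven days is equally likely to be used. Overlap caused by the Week 2 look-back would remain, so the SAP should also say whether a day may count in both weeks.

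The cost is a few lines of wording and programming. Some Week 1 values will rest on fewer than seven days and a few will become missing, which the MMRM accommodates.

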#### 4.2.11. Baseline definition

Baseline is defined as the data most recently collected prior to the first randomised treatment intake date/time. If time of the corresponding data (e.g. Questionnaires) is not collected then, we will assume that the assessment at Visit 3 is performed as planned, i.e. prior to the treatment intake.

The baseline assessment for hot flushes will be calculated using the last 7 days (not necessarily consecutive days) with an available data in the evening and/or the morning of the baseline diary completion period. A diary day is comprised of the evening entry of this day and the morning entry of the following day, in that order.

Mean daily frequency = Sum of number of hot flushes filled in the diary during the last 7 diary days (with at least one available data in the evening and/or morning) divided by 7.

Mean weekly severity = (number of moderate hot flushes for 7 days) x 2 + (number of severe hot flushes for 7 days) x 3] / (total number of moderate to severe hot flushes over 7 days).

Mean daily HF score = Sum of (frequency x severity) filled in the diary during the last 7 days (with at least one available data in the evening and/or morning) divided by 7. Severity is graded by the women from 1 to 3 (1 = mild; 2 = moderate; 3 = severe).

For the primary efficacy endpoint analyses and several of the secondary endpoint analyses, only moderate and severe HF data are included in the calculations. For these analyses the mild data recorded in the diary will be excluded from the baseline values.

A diary day comprises an evening entry and a morning entry, in that order. If a diary has been completed on a particular day but is missing data on HF that day, then it will be assumed that there was no HF on that day. This diary will not be used for the 7 days of baseline data. Only diary with available data will be used in baseline derivation.

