- (ii) a model based on isotonic regression (T-stat)

The models have been developed using the following prior assumptions:

1) On frequency of hot flushes:

- The mean reduction in the mean daily number of moderate and severe HF's in the placebo group is 4 per day
- Two target levels of test treatment: mean reduction from baseline in the mean daily number of moderate and severe HF's of 6 and 8
- Common standard deviation (SD) of 4.4
- Stopping guidelines for Emax if (a) the probability is > 90% that the mean hot flush reduction is at least 8 at that dose, or (b) the probability is <20% that the mean hot flush reduction is at least 5 (i.e., >80% probability that the mean hot flush reduction is <5).

2) On severity of hot flushes:

- The mean reduction in the severity of moderate and severe HF's in the placebo group is 0.44 per day
- Two target levels of test treatment: mean reduction from baseline in the severity of moderate and severe HF's of 0.66 and 0.88
- Common standard deviation (SD) of 0.55
- Stopping guidelines for Emax if (a) the probability is > 90% that the mean severity hot flush reduction is at least 0.88 at that dose, or (b) the probability is <20% that the mean severity hot flush reduction is at least 0.22 (i.e., >80% probability that the mean hot flush reduction is <0.22).

Emerging data (mean change from baseline in the frequency/severity of moderate and severe HF at Week 4) will be entered in COMPASS software using the Execute module. The following steps will be followed:

- Raw data from eDiaries will be provided to the Cytel blinded team by ERT, the CRF data will be provided by the Pharm Olam Data Management team
- Efficacy endpoints to be presented (see above) will be generated by the Cytel blinded team using the derivation described in this SAP
- Statistical descriptive tables for these endpoints will be produced by the Cytel blinded team using a dummy randomisation list

- Programs will be rerun by the Cytel unblinded team using the real randomisation list provided to the Cytel unblinded statistician
- Endpoint data for each patient along with their treatment arm will be entered into COMPASS.

Prior distributions, defined above and used for the simulation, will also be entered in the software. COMPASS has been developed as a software package for design of adaptive early stage trials within Cytel's suite of software programs for design, analysis, and implementation of clinical trials.

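### The SAP scores severity in two incompatible ways, and one of its severity planning pairs cannot occur on the scale that the final analysis points to

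*SAP*

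**What the plan says.** Two of the four co-primary endpoints are change in severity of moderate and severe flushes, at Weeks 4 and 12 (Protocol 8.1 and 11.9.1; SAP 2.5.1.1).

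- **Final analysis.** SAP 4.6.1 states: "The methods for calculating the endpoint are the same as described in section 4.2.11". SAP 4.2.11 has a single severity formula. Its numerator is "number of moderate hot flushes for 7 days) x 2 + (number of severe hot flushes for 7 days) x 3" and its denominator is "total number of moderate to severe hot flushes over 7 days". On mild flushes it adds: "For these analyses the mild data recorded in the diary will be excluded from the baseline values". It has no rule for a woman with no moderate or severe flush.
- **Section 4.3.2, under Interim Analyses.** "Mean weekly severity at each study visit will be calculated using the following": mild, moderate and severe flushes weighted 1, 2 and 3, divided by the "total number of mild, moderate and severe hot flushes over 7 days". It continues: "If the number of hot flushes is equal to 0, then the mean severity will be set to 0".
- **Planning values.** The same section sets the inputs for the Emax and T-statistic algorithms: "Two target levels of test treatment: mean reduction from baseline in the severity of moderate and severe HF's of 0.66 and 0.88", a placebo reduction of 0.44, a common SD of 0.55, and Emax stopping guidelines at 0.88 and 0.22. SAP 4.3 attributes 0.66 and 0.88 to RELENT-1.

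The end of SAP 4.6.1 reuses the 4.3.2 methodology for the optional Emax and trend analyses at Weeks 4 and 12. SAP 5 reports no changes from the protocol and does not mention the two formulas.

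**The concern.** The two formulas measure different things. Under 4.2.11 a flush that becomes mild drops out of the average instead of lowering it, so the score is 2 plus the severe share among the moderate and severe flushes that remain. Under 4.3.2 the same flush stays in and pulls the average down. A programmer following 4.6.1 and one following 4.3.2 would derive different co-primary data from the same diaries. They would also treat the best responders differently: undefined in one case, 0 in the other.

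Two things are at stake. Protocol 11.1.1 asks for significance on all four co-primaries before a firm conclusion is drawn, so the meaning of the two severity endpoints matters. And the severity targets and stopping guidelines are absolute reductions that inform dose allocation, so they have meaning only on a stated scale.

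**Working it through.** **Inputs.** Both formulas and the values 0.44, 0.66, 0.88, 0.22 and 0.55 are from the SAP sections named above. Mean baseline severity is not given in the documents, so a range of 2.2 to 3.0 is used as an assumption. The plan gives no derivation or power for its severity values, so there is no severity figure to reproduce. Its pairwise frequency figure (33 per group for 95% power, difference 4, SD 4.4) does reproduce, at 95.3% by the exact t calculation, but does not bear on this point.

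**Range on the 4.2.11 scale.** With m moderate and s severe flushes the score is (2m + 3s)/(m + s) = 2 + s/(m + s), which lies in [2, 3]. The largest reduction is baseline minus 2:

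| Mean baseline | 2.2 | 2.4 | 2.5 | 2.6 | 2.8 | 3.0 |
|---|---|---|---|---|---|---|
| Largest mean reduction | 0.2 | 0.4 | 0.5 | 0.6 | 0.8 | 1.0 |

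A mean reduction of 0.22 therefore needs a mean baseline of at least 2.22; 0.44 needs 2.44, 0.66 needs 2.66 and 0.88 needs 2.88. At each minimum no severe flush may remain.

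**Can 0.88 go with SD 0.55?** Change lies in [-1, 1]. For a variable bounded by a and b with mean μ, the variance is at most (b - μ)(μ - a). For a mean reduction of 0.88 this is (1 - 0.88)(0.88 + 1) = 0.12 × 1.88 = 0.2256, so the SD is at most 0.475. The pair 0.88 with 0.55 is impossible, whatever the baseline. For 0.66 the bound is √(0.34 × 1.66) = 0.751, so that pair is not excluded.

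**The same diaries under both formulas.** Baseline is 6 moderate + 4 severe, 24/10 = 2.40 on either.

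| Diary at the visit | 4.2.11 score (change) | 4.3.2 score (change) |
|---|---|---|
| All moderate become mild | 12/4 = 3.00 (+0.60) | 18/10 = 1.80 (-0.60) |
| Half of each become mild | 12/5 = 2.40 (0) | 17/10 = 1.70 (-0.70) |
| All severe become mild | 12/6 = 2.00 (-0.40) | 16/10 = 1.60 (-0.80) |
| All become mild | 0/0, undefined | 1.00 (-1.40) |
| No flushes | 0/0, undefined | 0 (-2.40) |

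**Range on the 4.3.2 scale.** For baselines of 2.2 to 3.0 the largest reduction is 1.2 to 2.0 if all flushes become mild, and 2.2 to 3.0 if there are none. Both targets are attainable there.

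**Mixing the two.** If baseline follows 4.2.11 and visits follow 4.3.2, take an unchanged diary of 3 mild, 6 moderate and 4 severe flushes. Baseline is 24/10 = 2.40 and the visit score is (3 + 12 + 12)/13 = 27/13 = 2.08, an apparent reduction of 0.32 with no change in symptoms. Randomisation gives this offset the same expectation in each arm, so it mainly distorts within-arm change. The interim targets and Emax stopping guidelines are within-arm changes.

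**The case against.** The strongest reply is that 4.3.2 supplies what 4.2.11 lacks. Its formula is worded for each study visit, it has a zero rule, it sits beside the planning values, and SAP 3.2 takes from it the rules for the days used in the frequency and severity analysis. On that scale 0.66 and 0.88 are within range. This stands far enough to rule out treating 4.2.11 as the settled definition. It does not remove the problem: SAP 3.2 borrows only the day rules, 4.6.1 points to 4.2.11, and the planning values are labelled as severity of moderate and severe flushes. Combining the 4.3.2 visit score with the 4.2.11 baseline creates the 0.32 artefact.

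A reader might infer more than the documents support:

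- **That the score can never fall below 2.** The 4.3.2 formula goes to 1, or to 0 with no flushes.
- **That the targets are out of reach.** This depends on a baseline that is not given. Protocol 10.2.1 grades a waking night flush as severe, which raises baseline, and 4.2.11 allows reductions up to 1.0. If the zero rule were added to 4.2.11, with every other woman at exactly 2, a mean reduction r at baseline b would need a share (r - (b - 2))/2 scored 0. For 0.88 that is 24% at 2.4 and 19% at 2.5; for 0.66 it is 13% and 8%.
- **That every shift to mild is missed.** Severe-to-mild shifts lower the score, and any moderate or severe flush that turns mild is credited in the frequency co-primary.
- **That the four-endpoint requirement will fail.** Nothing here is a power figure. In one illustration (assumed baseline 10% mild, 55% moderate, 35% severe; latent normal shift of 0.5 SD on placebo and 1.0 SD on active) the 4.2.11 score falls from 2.389 to 2.240 and 2.136. The direction is right and the arms differ by 0.10, against 1.971 - 1.694 = 0.28 over all flushes.

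**Conclusion.** The concern holds as a conflict between two stated severity scores. Three results need no assumption about the data: the 4.2.11 score is confined to 2 to 3 and is undefined with no moderate or severe flush; moderate-to-mild shifts raise it and proportional shifts leave it unchanged; and a mean reduction of 0.88 with SD 0.55 cannot occur on it (SD at most 0.475, mean baseline at least 2.88). The mixed reading adds an apparent reduction whose size depends on the share of mild flushes at baseline, 0.32 in the example. How far 0.44 and 0.66 fit the 2-to-3 scale depends on the unknown baseline severity. The scale behind the RELENT-1 figures cannot be seen from these documents.

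**What to change.** Before unblinding:

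1. State one severity formula for the co-primary in SAP 4.2.11, 4.3.2 and 4.6.1, used at baseline and at every visit, with an explicit rule for a woman with no qualifying flush.
2. Put the placebo value 0.44, the targets 0.66 and 0.88, the 0.22 limit and the SD 0.55 on a stated scale. Either give the algorithms all-flush severity at both baseline and Week 4, or restate the values for the 2-to-3 scale. This also covers the Emax and trend analyses in 4.6.1.
3. Keep the protocol's co-primary label. When drawing a severity conclusion, show the all-flush severity MMRM contrast at Weeks 4 and 12 beside it (already planned in SAP 4.6.2.1). That section also refers back to 4.2.11, which has no all-flush severity formula, so write that one out too.

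Making all-flush severity the co-primary would replace a protocol-defined endpoint. That is a debatable trade-off and is not needed here.

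The cost is SAP wording and minor reprogramming. The restated planning values may look less favourable. SAP 3.1 and 4.6.2.7 indicate that the blinded data review has taken place. If the interim reviews are also complete, the SAP or report should record which formula they used; items 1 and 3 still apply to the final analysis.
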